The second step of recruitment: The subjects of the study will be selected during c-section by purposive sampling and only those subjects who will fulfil perioperative criteria of the study will be selected. The primary surgeons of the C-section will be 2nd and 3rd-year residents of Lady Willingdon Hospital. If dense adhesions will be encountered during opening the peritoneal cavity or before the separation of bladder flap, the primary surgeons will hold the operation and call the principal surgeon (Assistant [name] and Gynaecology) to carry out adhesiolysis and complete the operation. The Principal surgeon will examine the adhesions and enrol the subjects in the study and perform randomization according to the random number envelop if perioperative criteria for adhesions will be fulfilled. (See [Entry Form](#))

The same Principal surgeon will recruit subjects after carrying out grading of adhesions, perform adhesiolysis and complete the operation with primary surgeons to avoid bias.(See [Fig 1](#))

Randomisation procedure

The Principal surgeon will randomize the calculated sample size into cysto-inflation and control groups by parallel assignment. They will write the random numbers (downloaded from the internet) on closed envelopes with the assigned groups inside. The closed envelopes will be serially placed with the smallest number uppermost, in random number file. The file will be kept in the safe custody of theatre in-charge nurse before starting recruitment for the study. If the women will fulfil the eligibility criteria, the Principal surgeon will recruit her in the study. The theatre in charge nurse will take out uppermost envelope from the subject's file. She will be open the envelope and disclose the group to the principal surgeon. Then, she will close the envelope again and place it below all the envelopes. The theatre staff nurse will also provide the setup for cysto-inflation. At the end of the operation, she will get the Entry Form signed by the Principal surgeon and hand it over to the study team. The study team medical officers in the theatre will enter the random number of each subject on her documents including Hospital Admission File, Consent Form, Trial Entry Form and Outcome Form.

Blinding

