We will perform Statistical analysis by using IBM spss statistics 20 (SPSS Inc, Chicago, IL, USA). The characteristics of the subjects will be analyzed as continuous data or ordinal data. Normality of continuous data will be analyzed by the Shapiro Wilk test. The normal baseline data will be compared by T-test, non-normal data by Mann Whitney U test and ordinal data with the chi-square test. The outcome of both groups will be calculated as numbers (percentages) by descriptive statistics. The effect of cysto-inflation on outcome data will be analyzed using regression analysis. The same problem experienced by the same subject will be recorded only once on the spss datasheet. There will be no second entry if the subject presents with the same problem again. The data for any subject who do not come for follow up after discharge will be used and analyzed in study characteristics but will be excluded from the analysis of results. The power of the study for bladder injury will be calculated with statistical software G'Power version 3.1.

Adverse events

The study team will be responsible to record all adverse events and serious adverse events to the subjects of the study, related to or not related to the intervention. The team members will ask open probing questions to enhance the quality of the collected data. An adverse event is

defined as any undesirable experience during follow-up leading to contact with the healthcare system (general practitioner or hospital). If adverse event results in hospitalisation, prolonged inpatient hospital care, result in re-surgery, or if an adverse event is life-threatening, result in death, permanent disability or damage, they will be categorised as serious adverse events. Adverse Events will be recorded in the adverse events reporting register. The study team will report all expected and unexpected adverse events in the study population to the principal investigator in monthly meetings to assess their potential consequences.

Data Management Plan

Documents safety

All the documents, together with the numbered envelopes and the completed forms will be stored in folders that will be kept in the locked research office of the principal investigator with access limited to authorised persons. The study team will ensure that all variables from the completed forms are continuously entered into SPSS 20 datasheet.

Data monitoring

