The study will not have a formal data monitoring committee as no serious adverse events are related to or have been observed previously by implication of this intervention in the hospital. Any unexpected serious adverse events or outcomes will be discussed by the trial management committee (study team). Furthermore, the trial management committee will monitor recruitment, intervention and follow up rates and any concerns related to the study.

Data safety

Once the trial is completed, all material belonging to the study will be stored in the research office. Collected data will be retained in the custody of the principal investigator till compilation of results by statistician so that any missing piece of information can be acquired from the data file.

Data Destruction Plan: To minimize the risk of breach of confidentiality, we will not use the subject's name or hospital number to identify them on any study records. Instead, a study number will be assigned to each subject according to the random number envelope. This number will be used to study documents that relate to the subject and to enter data in spss. We will keep the list of random number groups in a secure, locked location. At the end of the project, this list will be destroyed. All personal data will also be destroyed at the end of the trial to protect confidentiality before, during and after the trial.

Quality assurance: The study team will arrange a monthly quality assurance meeting with the principal investigator. All the problems faced during the consent, theatre management and conducting the postoperative surveys of the patient will be discussed. The solutions should be sought for each problem and refinements will be implemented if needed. The data collection and management procedures of the study have been approved by the king Edward medical university, Pakistan.

Ethics, dissemination and perspectives of the study

Ethics

The study is a part of the project "Cysto-inflation Versus deflation to prevent bladder injury in OBG (obstetrics and gynaecology) surgery" approved by the ethical committee of King Edward Medical University, Pakistan with ERB#216/RC/KEMU on 27 March 2017 and will be conducted in accordance to the Helsinki declaration. Personal information about patients will be kept separate from the main dataset and will not be shared.

Dissemination

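### Used allocation envelopes are re-closed and returned to the live file with no seal, opening record or planned count, so an early opening would leave no trace

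*Combined protocol and SAP*

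**What the plan says.** All references are to the combined protocol and SAP.

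The Randomisation procedure section describes how the envelopes are made: "They will write the random numbers (downloaded from the internet) on closed envelopes with the assigned groups inside". They are then ordered: "The closed envelopes will be serially placed with the smallest number uppermost, in random number file". The theatre in-charge nurse holds the file. When a woman qualifies during her operation, "The theatre in charge nurse will take out uppermost envelope from the subject's file". Next, "She will be open the envelope and disclose the group to the principal surgeon". The section then disposes of the used envelope: "Then, she will close the envelope again and place it below all the envelopes".

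The same section has medical officers copy the random number onto four of the woman's documents. The Data Destruction Plan makes that number her identifier: "a study number will be assigned to each subject according to the random number envelope". The Entry Form has fields for date of operation, time of operation, random number and the principal surgeon's signature, which is obtained when the operation is over.

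No section mentions opacity, a seal, a mark for a used envelope, a note of when it was opened, or a reconciliation of envelopes with enrolled women.

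**The concern.** Under envelope allocation, the state of the envelope is the main physical evidence that nobody saw the next assignment before the woman was enrolled. An opened flap normally shows that the contents have been read. Here closing the flap again is part of the routine, so a closed envelope no longer shows that it is unread. Used envelopes also go back into the same file as unused ones.

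This matters because enrolment depends on a judgement made in theatre. The principal surgeon grades the adhesions and decides whether the perioperative criteria are met. Knowing the next group could influence that decision. The Blinding section says that assignment will be hidden from surgeons before the operation. The envelope procedure leaves no means of showing afterwards that it was.

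**Working it through.** The plan gives no figure on this point. The check follows an envelope through the written procedure and asks what trace each kind of irregularity would leave.

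**Inputs.** The Sample size section gives 214 women, 107 per group. The number of envelopes is not stated. I take N = 214, because the Randomisation procedure says that the calculated sample size is what gets randomised. The file starts in ascending order, each draw is from the top, and each used envelope goes to the bottom.

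**Can a used envelope come up again?** In an undisturbed file, draw i takes the i-th envelope for every i up to N. Repeats after n draws = max(0, n − N).

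- n = 214: 214 − 214 = 0 repeats. The first possible repeat is draw 215.
- n = 220: 220 − 214 = 6 repeats.
- n = 236: 236 − 214 = 22 repeats.

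The last two are illustrations; the plan is to enrol 214.

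An earlier repeat needs the order to be lost. If the file were fully shuffled after m draws, the chance that the next envelope is already used would be m/N: 21/214 = 9.8%, 107/214 = 50%, 160/214 = 74.8%. If it were put back into ascending order, the top envelope would be a used one, since the smallest numbers go first. The documents describe neither event.

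**What trace would each irregularity leave?**

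| Irregularity | Trace under the written procedure | Check planned |
|---|---|---|
| Envelope opened early, read, re-closed and left in place | None. It is later drawn in its proper turn, so number, date and time all look right | None |
| Same envelope used for two women | Two women share one study number | None |
| Envelope drawn out of order | Random numbers fail to rise when Entry Forms are sorted by operation date and time | None |
| Used and unused envelopes confused | The fall from highest to lowest number marks the boundary, while file order is kept | None |

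The first row differs in kind from the rest. The forms record which number was used and when the operation took place. They do not record when the envelope was opened, so no later comparison of forms can reveal an early opening.

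**The case against.** The strongest reply is that the procedure has more built-in order than it first appears. Each envelope carries its own number, the file is ascending, and each number is copied to several documents. A repeat would produce a duplicate identifier, and an out-of-order draw would show against the operation dates and times. This stands. It limits the point on those two irregularities to the absence of a planned check; detection is possible.

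A reader might infer that a used allocation can simply be issued again. The written sequence does not allow that within 214 draws. Nor does the Documents safety section describe a re-sort. It says "All the documents, together with the numbered envelopes and the completed forms will be stored in folders", in the principal investigator's locked office, which is a different place from the nurse's custody. It does not say that unused envelopes move there during recruitment.

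A reader might also infer that a woman's arm could not be confirmed. The documents do not support that. Her number is on her records, and the Blinding section has a random number list going to the statistician. The list is destroyed only at the end of the project.

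A further reply is that closed may mean glued in practice, so that a tampered flap would show. That may be so, but the protocol does not say it, and an instruction to close the envelope again suggests a closure that can be remade.

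Finally, the principal surgeon is said to randomise the sample, decides eligibility and operates, so foreknowledge might not require opening an envelope. That is a separate and larger weakness. It reduces what this repair can achieve but does not make the envelope procedure sound.

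**Conclusion.** The point holds in limited form. Routine re-closing, with no stated seal and no opening record, means that an envelope read early and closed again cannot be told from an untouched one. Used and unused envelopes are kept apart by file order alone. Repeated or out-of-order draws are traceable, but no one is assigned to trace them.

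The absence of repeats in the first 214 draws rests on two assumptions: 214 envelopes and an undisturbed file. The frequency of mishandling is unknown, and the documents give no basis for estimating bias.

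A reader might infer that one misdraw could reverse the conclusion, because the Project summary calls the technique effective if the injury proportion is below half of control. With supposed counts of 5/107 v 11/107 the ratio is 45.5%; moving one injured woman across gives 6/108 v 10/106, or 58.9%. This does not measure the present weakness. The counts are invented and were placed next to the threshold. A misdraw would also change the treatment a woman receives, with unknown effect on injury, whereas the example only relabels her.

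I would class this as a cheap improvement of minor severity.

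**What to change.** Replace the sentence on re-closing with:

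> Envelopes are opaque and sealed with a signature across the flap. At opening the nurse writes the date, time, study number and her signature on the envelope; it is not re-closed or returned to the file but kept in a separate locked box. Opened and unopened envelopes are counted against Entry Forms at each monthly quality meeting.

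The seal is the essential part. Signing and boxing opened envelopes would not by itself reveal one that had been read early. At each count, opened envelopes should equal women randomised, opened plus unopened should equal the number prepared, and the flaps of unopened envelopes should be intact.

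The cost is a second locked box, a few seconds of writing per woman, slightly more paperwork in theatre, and one agenda item at a meeting that the Quality assurance section already schedules. Sample size and patient care are unaffected. The change does not cure the principal surgeon's combined role in preparing the allocation, deciding eligibility and operating, which needs its own remedy.

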Title of the study	A randomized controlled trial of Cystoinflation to prevent bladder injury in the adhesive disease of multiple caesarean sections
Registration #	NCT04302545
ERB reg #	Reg # 216/RC/KEMU.
Document Date	March 27,2017
Principal Investigator:	[name] , FCPS; Obstetrics & Gynaecology. Assistant Professor (Obstetrics & Gynaecology), King Edward Medical University /Lady Willingdon Hospital, Lahore, Pakistan
Co-Investigators:	
 • [name], MS trainee (Obstetrics & Gynaecology), King Edward Medical University /Lady Willingdon Hospital, Lahore, Pakistan • [name], FCPS trainee (Obstetrics & Gynaecology), King Edward Medical University /Lady Willingdon Hospital, Lahore, Pakistan • [name], FCPS trainee (Obstetrics & Gynaecology), King Edward Medical University /Lady Willingdon Hospital, Lahore, Pakistan • [name], Director of Medical Education, Institute of Public Health Pakistan
Settings:	Lady Willingdon Hospital Lahore, Pakistan

Study protocol: “**A randomized controlled trial of Cystoinflation to prevent bladder injury in the adhesive disease of multiple caesarean sections**”

Project summary

Background: Repeated caesarean sections (C-section) carry the risk of bladder injury due to the formation of adhesions obscuring pelvic planes. Distension of Bladder by retrofill (Cystoinflation) is a useful technique to identify bladder margins. We hypothesize that cystoinflation can prevent bladder injury in dense adhesions of previous C-sections by improving identification of bladder outline.

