Method: We will find out the effectiveness of cystoinflation by conducting a prospective randomized controlled trial in Lady Willingdon Hospital, a university-affiliated teaching hospital in Pakistan, for two years, including a follow-up period of three months. The subjects of the study will be two hundred and fourteen healthy pregnant women with previous operative deliveries which during their C-section, prove to have dense bladder adhesions. The subjects will be randomized into cystoinflation and control groups. Preoperatively, the study team will counsel the women and take informed consent to include them in the study if dense adhesions were found during their C-section. The surgeon will perform adhesiolysis after identifying bladder during retro-fill (with 300cc saline) in the cystoinflation group and without retro-fill in control. The primary outcome will be assessed by bladder injury rate, blood loss and operative time and secondary outcome by postoperative urinary tract infection, micturition problems and fistula formation. Cystoinflation will be considered effective if the proportion of bladder injury in cystoinflation group will be less than 50% of the control.

Discussion: The routine practice of preoperative insertion of urinary catheter fails to prevent bladder injury in multiple C-sections. A few scientists have successfully used cystoinflation technique to prevent bladder injury in pelvic adhesive disease. In this study, we have used cystoinflation in dense adhesions of previous C-sections. The findings of this study may support the previous studies and may serve as a trigger for ongoing research of surgical techniques to prevent iatrogenic bladder injury.

Study protocol: “A controlled study of Cystoinflation to prevent bladder injury in the adhesive disease of multiple caesarean sections”

erb registration: The institutional review board of King Edward Medical University, Pakistan
Reg # 216/RC/KEMU.

Principal Investigator: [name], FCPS; Obstetrics & Gynaecology. Assistant Professor (Obstetrics & Gynaecology), King Edward Medical University /Lady Willingdon Hospital, Lahore, Pakistan

Co-Investigators:

- [name], MS trainee (Obstetrics & Gynaecology), King Edward Medical University /Lady Willingdon Hospital, Lahore, Pakistan
- [name], FCPS trainee (Obstetrics & Gynaecology), King Edward Medical University /Lady Willingdon Hospital, Lahore, Pakistan

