Control group: The subjects assigned to the control group will undergo no intervention. The Principal surgeon will perform adhesiolysis by the same traction counter-traction method with urinary catheter put on free drainage throughout the C-section.

If there will be a suspicion of bladder injury in either group, it will be confirmed by performing the retrograde dye test with methylene blue and injury will be repaired by the Principal surgeon.

Crossover

There is no possibility of crossover in this study as subjects will be selected during operation and the women who refuse to be included in either group preoperatively will be excluded from the study before group assignment.

Data collection procedure

Data will be collected at the time of admission (baseline), during surgery, on the 3rd postoperative day, at the time of discharge from the hospital and the end of three month follow-up period (for those enrolled in the study). The subjects will be advised to report for any postoperative fever or micturition problem during follow-up. Their visits will be recorded on follow up form by the study team medical officers specifically trained in correctly interpreting the problems of the subjects and filling the outcome form (See [Outcome](#) Form).

Baseline Data

The entry form will include baseline data consisting of demographic features and characteristics of the subjects recruited in the study. The demographic features will include age, gestational age, parity, socioeconomic status, and the number of previous C-sections. The other characteristics will be the score of adhesions and preoperative postmicturition bladder volume. The allotted random number will be entered in entry form of the subject and will be signed and kept in a locked place by study team manager in the theatre. (See [ENTRY FORM](#))

Outcome

Primary outcomes will be the bladder injury rate, the extent of the injury, operative time, blood loss and proportion of subjects receiving blood transfusion.

The bladder injury: The bladder injury will be detected by direct observation during surgery. The suspected bladder injury will be confirmed with the dye test and will be reported as the bladder injury rate and extent of injury.

- A. Bladder injury rate will be recorded as the percentage of subjects with bladder injury in each group.
- B. The extent of the injury will be analyzed by the size, site and depth of injury.

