 - i. The size of the injury will be measured in centimetres with a sterilized scale.
 - ii. The site of injury can either be the dome of the bladder, the posterior bladder wall, the trigone or one or both ureters.
 - iii. Depth of injury will be taken as layers involved i.e. either involving muscular layer partly or completely with intact mucosa or full depth injury (perforation).
 - iv.

Operative Time: The staff nurse will record the duration of surgery as time in minutes from incision to closure of the skin.

Blood Loss: The estimated blood loss will be determined by the increase in weight of sponges used during the operation, taking 1 gram equal to 1cc of blood and the number of subjects who received blood transfusion during operation.

Secondary Outcomes

Postoperatively, subjects will be assessed for urinary tract infection (UTI), micturition problems, and fistula formation during the hospital stay and for the next three months. Duration of catheterization and hospital stay will also be recorded. The outcome of each subject will be noted on a Performa by assigned medical officers during the hospital stay and the follow-up period and entered in SPSS20 datasheet.

1-Urinary tract infection (UTI) markers will be more than 10pus cells/hpf in urine or urine showing infectious organisms on culture on the third postoperative day.

- A. **Dysuria** will be expressed by the subject as painful micturition using an 11point Numeric Rating Scale ICCs (.673-.825), $r=.7-.99$. (0 No Pain, 1-3 Mild Pain, 4-6 Moderate Pain, 7-10 Severe Pain).
- B. **Other micturition problems** (feeling of incomplete evacuation, frequency, urgency, urethral and extra-urethral incontinence) will be measured subjectively on Likert scale questionnaire (0-never, 1-rarely, 2-sometimes, and 3-often) and analyzed as a composite variable in spss. Urinary retention will be diagnosed if post-micturition bladder volume is >50cc on ultrasonography on the day of discharge from the hospital.

- I. **Feeling of incomplete evacuation:** It is the feeling created by incomplete emptying of the bladder. The subject will be inquired about the feeling of full bladder accompanying it.
- II. **Urgency** will be diagnosed as a sudden urge to urinate.
- III. **Frequency** Needing to pass urine more than seven times in 24hours.

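### The summary names three primary outcomes and the Outcome section five, with no formal ranking or multiplicity rule, and the summary's bladder-injury criterion is not carried into the outcome and analysis sections

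*Combined protocol and SAP*

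**What the plan says.** The Method paragraph of the Project summary gives three items: "The primary outcome will be assessed by bladder injury rate, blood loss and operative time". The Outcome section gives five: "Primary outcomes will be the bladder injury rate, the extent of the injury, operative time, blood loss and proportion of subjects receiving blood transfusion". Extent of injury and transfusion appear only in the second list.

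The two added items are not wholly new. The Outcome section says that bladder injury "will be reported as the bladder injury rate and extent of injury", and the Blood Loss definition combines sponge weight, "taking 1 gram equal to 1cc of blood and the number of subjects who received blood transfusion during operation". Extent has three parts: "The extent of the injury will be analyzed by the size, site and depth of injury".

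Three statements single out bladder injury:
- Success criterion (Project summary, Method): "Cystoinflation will be considered effective if the proportion of bladder injury in cystoinflation group will be less than 50% of the control".
- Hypothesis (Project summary, Background): "We hypothesize that cystoinflation can prevent bladder injury in dense adhesions of previous C-sections by improving identification of bladder outline".
- Power (Statistical analysis): "The power of the study for bladder injury will be calculated with statistical software G'Power version 3.1".

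The closing paragraph of the Background, however, gives reduction of both bladder injury and blood loss as the aim. For the effect on outcomes, the Statistical analysis section offers percentages and an unspecified regression analysis. It sets no significance level, order of testing, co-primary rule or adjustment. The Blinding section refers to a primary analysis by an independent statistician, but no section defines that analysis.

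**The concern.** Two current sections disagree about which outcomes are primary, and neither ranks its list. The one statement that settles what counts as *effective* sits in the summary, has no test attached, and does not reappear where outcomes and analysis are specified. A statistician working from the Outcome and Statistical analysis sections would find five outcomes of equal standing and no rule for reading them together.

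Two things are at stake. The first is the error rate: several primary tests without a rule give a chance above 5% that at least one is significant when nothing differs. The second is interpretation. If bladder injury is inconclusive and blood loss or operative time reaches significance, the plan lets the latter be reported as a primary result while the trial's own question stays open. Nor does it say how to read a mixed result, such as fewer injuries with longer surgery.

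**Working it through.** The plan states no overall error rate, so there is no figure of its own to reproduce.

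**Inputs**
- Number of primary outcomes: 3 (Project summary) or 5 (Outcome).
- Level per test: 0.05, two-sided. This is an assumption. The Sample size section gives 95% confidence for the sample size; the Statistical analysis section gives no level.
- Correlation between outcomes: not in the documents; assumed, and varied below.

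**Step 1. Independent tests, no true difference on any outcome.** Chance of at least one false positive = 1 − (1 − 0.05)^k.
- k = 3: 1 − 0.95³ = 1 − 0.8574 = 14.3%.
- k = 5: 1 − 0.95⁵ = 1 − 0.7738 = 22.6%.

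Leaving bladder injury aside, the chance that at least one of the *other* listed outcomes is falsely significant is 1 − 0.95² = 9.8% (three-item list) or 1 − 0.95⁴ = 18.5% (five-item list).

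**Step 2. Correlated tests.** Test statistics were simulated as equicorrelated standard normals (400,000 draws), counting draws in which any |Z| exceeds 1.96.

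| Assumed correlation | 3 outcomes | 5 outcomes |
|---|---|---|
| 0.3 | 13.7% | 20.9% |
| 0.5 | 12.6% | 18.2% |
| 0.8 | 9.8% | 12.7% |

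A positive correlation is to be expected, because extent belongs to injury and transfusion to blood loss. The independent figures are therefore upper illustrations.

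**Step 3. Sensitivity to the injury test.** The plan names no test for injury. With 107 per arm and an assumed true rate of 5% in both arms, Fisher's exact test at nominal 5% has true size 2.24%. Putting that in for one of the independent tests:
- k = 3: 1 − 0.9776 × 0.95² = 11.8%.
- k = 5: 1 − 0.9776 × 0.95⁴ = 20.4%.

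An uncorrected chi-square test stays near 4–5% at low rates, so Step 1 then changes little.

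**Step 4. What an alpha split would cost.** Bonferroni levels are 0.05/3 = 0.0167 and 0.05/5 = 0.01. Take about 97 evaluable women per arm (107 ÷ 1.1 = 97.3) and a halving of the injury rate, using the two-proportion normal approximation. For 80% power the control injury rate must be about 35% at 0.05, 43% at 0.0167 and 47% at 0.01. With bladder injury as the only primary outcome, no split is needed.

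**The case against.** The strongest reply is that the plan already has a lead outcome. The title, hypothesis, success criterion and power statement all concern bladder injury. A reader might infer from the two lists that a chance finding on any item would make the trial a success. The documents do not support that: a false positive on operative time, blood loss or transfusion cannot meet the stated criterion. This part of the reply stands, and it limits the point to what may be *labelled* a primary result. It does not remove the point, because the criterion appears only in the summary, carries no test, and sits beside a Background aim that also names blood loss.

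Second, the five items largely write out the summary's three domains. That is correct and makes the conflict smaller. But the Outcome section still names all five as primary, so the texts need reconciling.

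Third, a reader might count size, site and depth separately and arrive at seven tests with an error of 1 − 0.95⁷ = 30.2%. That figure should not be used. The plan does not say these get separate tests, and they exist only in injured women, so treating them as independent comparisons is not credible.

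Fourth, it is tempting to argue that injury is rare and that operative time and blood loss are therefore the outcomes most likely to reach significance. The low rates in the Background are for caesareans in general. No rate is given for women whose dense adhesions hide the bladder, so that argument rests on an unstated figure and is not relied on here.

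Finally, a single primary outcome is not the only remedy; an alpha split or a fixed testing sequence would also control error. That is true, but a split costs power on the one outcome that the success criterion uses.

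**Conclusion.** The point holds in limited form. The primary lists differ (three against five), no ranking or multiplicity rule is stated, and the bladder-injury criterion is confined to the summary. A chance result on another listed outcome could be reported as a significant primary outcome, though not as showing the technique *effective* in the plan's sense.

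Under an inferred two-sided 5% per outcome, the overall false-positive chance is at most about 14.3% (three) or 22.6% (five), and about 12.6% or 18.2% at an assumed correlation of 0.5. It stays above 5% for every correlation examined. The discrepancy and the missing rule can be read directly from the text; the size rests on the assumed level and correlations. This should be corrected, but it does not undermine the design.

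**What to change.** Make the same change in three places: the Method paragraph of the Project summary, the Outcome section and the Statistical analysis section.

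- Name bladder injury rate as the single primary outcome, with one stated test at two-sided 5%.
- Make operative time, blood loss and transfusion secondary, either Holm-adjusted or labelled exploratory.
- Report extent of injury (size, site, depth) descriptively among injured women. It is defined only after randomisation and in a subset, so it is not suited to a between-arm test.
- State that only the bladder injury result supports the word *effective*.

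The cost is wording; no extra patients or data are needed. The one downside is that blood loss and operative time can no longer carry a primary claim. If the investigators want to keep that option, they should specify a fixed sequence or alpha split instead and accept its cost.
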